## 10.0 SAMPLE SIZE AND POWER

Planned sample size:

**Phase 1 Escalation:** Approximately 18 subjects are planned to enroll: 3 to 6 subjects in Cohort 1; 3 to 6 subjects in Cohort 2; and 3 to 6 subjects in Cohort 3.

## Final Analysis Statistical Analysis Plan (SAP)

The sample size for Phase 1 is not based on power calculations, but rather on clinical judgement and the expectation that the objectives of this trial will be met with approximately 18 subjects enrolled in the 3+3 design.

### 11.0 ANALYSIS POPULATIONS

#### 11.1 Full Analysis Set

The Full Analysis Set (FAS) will include all subjects who received any amount of ELI-002-2P vaccine. This population will be used for summaries of subject demographics, and baseline characteristics. Additional exploratory analyses may be performed for the subjects treated at the MTD and doses lower than the MTD at which biomarker (ctDNA, or if ctDNA was not detected at baseline, serum tumor biomarker) clearance/reduction is observed.

Planned treatment received will be used for FAS.

#### 11.2 Safety Analysis Set

All subjects who received at least one dose of vaccine ELI-002-2P. This set will be used for the safety evaluation (AEs, clinical laboratory assessments, vital signs, ECGs, ECOG, PEs). No data will be imputed for the safety analysis set; only observed data will be summarized unless otherwise specified. Actual treatment received will be used for the Safety Analysis Set.

#### 11.3 Per protocol Set

The Per Protocol Analysis Set will include all FAS subjects who have no major protocol violations. The exclusion list for this set will be identified prior to database lock. Analysis on the Per Protocol Analysis Set will be performed if warranted.

All violations and exclusions of subjects from analysis sets will be identified through programmatic checks, through medical reviews, and by clinical research associates during site monitoring. Protocol deviations will be classified as key (important) or non-key (not important) prior to the database lock.

#### 11.4 PD (Pharmacodynamic)/Biomarker Evaluable Set (PDS)

The PD/Biomarker Evaluable Set will include subjects who receive any amount of trial treatment, with the additional requirement that relevant blood sampling data at the appropriate assessment time point(s) must be available for inclusion in the analysis for any PD parameter.

The PDS analysis set will be used for summary of Pharmacodynamic endpoints and biomarkers.

### 12.0 STATISTICAL CONSIDERATIONS AND ANALYSIS

#### 12.1 Derived Variables

The Table provide the list of derived variables for Demographic and baseline characteristics, various duration derivations, drug compliance, baseline derivations and other important derivations applicable for this study.

**Final Analysis  
Statistical Analysis Plan (SAP)**

**Table 8: Derived variables**

Variables	Formula
Demographic and Baseline characteristics	
Body mass index (BMI) (kg/m  )	weight (kg)/[height (m)] 
Derivation of Duration	
Study day at any visit	Date of interest – date of first dose of study treatment. One day is added if this difference is ≥ 0
Duration of study (Days)	(Date of study completion/discontinuation (for discontinued subjects) – date of first dose) + 1
Duration of Exposure to the study treatment ( weeks )	Is [last date of booster dose – first date of immunization dose] + 1] / 7. IF treatment discontinuation, then last date of booster dose = last dose date prior to or at the date of treatment discontinuation.
Treatment Exposure and Compliance	
Cumulative Planned volume (mL)	Total planned volume for each dose* Planned number of doses for the duration of exposure
Cumulative actual volume administered (mL)	Total actual volume administered from exposure CRF page (Cumulative value of 'Actual volume administered' from Study Drug Administration)
Expected Dose	Calculated as the expected number of vaccinations multiplied by assigned dose in mg
Compliance (%)	(Cumulative actual volume administered /Cumulative planned volume)*100
Dose intensity (DI) for ELI-002 Amph-Peptides 2P	Amount of actual cumulative dose of ELI-002 Amph-Peptides 2P (mg) divided by expected dose given for a full 10 course of vaccinations.
Dose intensity (DI) for ELI-002 Amph-CpG-7909	Amount of actual cumulative dose of ELI-002 Amph-CpG-7909 (mg) divided by expected dose given for a full 10 course of vaccinations.
Relative dose intensity	Cumulative dose received divided by expected dose and multiplied by 100
Baseline Derivations	
Baseline value	Unless otherwise specified, the baseline value is defined as the last non-missing observation prior to administration of the first dose of study treatment. For most assessments, this would be the Visit 3 value. If Visit 3 is missing, the Visit 2 value will be used.
Change from baseline	Post baseline value – Baseline value
Fold change from baseline	(Post baseline value – Baseline value)/Baseline value
Biomarker Reduction/Clearance	
Note: All reporting will select the biomarker (ctDNA, CEA, or CA-19) which contains the best (i.e., largest decrease post-baseline) result per subject. If there is no decrease for a given subject, then “best” is the smallest increase.	

**Final Analysis  
Statistical Analysis Plan (SAP)**


Clearance
	
Define as the percent change from baseline of the on-study ctDNA, or CA19-9, or CEA that achieved -100%.
 
Notes:
 
 
a. Clearance start will be the date of first clearance.
 
b. Once clearance start date is identified for a biomarker, the same biomarker will be used to determine the clearance end date.
 
c. Results will not be considered if a subject has already started taking subsequent anti-cancer therapy.
 
d. If there is a tie for best response across biomarkers, select ctDNA first.                             
 
▪ For PDAC subjects, select CA19-9 second, CEA third.
 
• For CRC subjects, select CEA second, CA19-9 third.
 
 
 

Reduction
	
Defined as the percent change from baseline of the on-study ctDNA, or CA19-9, or CEA that achieved any decrease (i.e., a negative percent change from baseline).
 
Notes:
 
 
a. Reduction start will be the date of first reduction.
 
b. Once reduction start date is identified for a biomarker, the same biomarker will be used to determine the reduction end date.
 
c. Results will not be considered if a subject has already started taking subsequent anti-cancer therapy.
 
d. If there is a tie for best response across biomarkers, select ctDNA first.                             
 
• For PDAC subjects, select CA19-9 second, CEA third.
 
• For CRC subjects, select CEA second, CA19-9 third.
 
 
 

Duration of Biomarker Clearance/Reduction
	

Clearance Duration
	
This is confirmed after clearance start by an increase above -100% change from baseline followed by a second increase above -100% at least 1 week afterwards.
 
Notes:
 
 
a. The end date will be the date of the first subsequent increase.
 
b. If the increase cannot be confirmed by a second increase, then the potential end date of biomarker clearance will proceed to the next increase and so on.
 
c. Subjects with confirmed clearance duration will not be censored.
 

Reduction Duration
	
This is confirmed after reduction start by an increase above the initial reduction followed by a second increase above the initial reduction at least 1 week afterwards.

**Final Analysis  
Statistical Analysis Plan (SAP)**

	
Notes:
 
 
a. The end date will be the date of the first subsequent increase.
 
b. The second increase may be above or below the first subsequent increase as long as it is above the first documented reduction.
 
c. If the increase cannot be confirmed by a second increase, then the potential end date of biomarker reduction will proceed to the next increase and so on.
 
d. Subjects with a confirmed reduction duration will not be censored.
 

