### **1.4. Data Analysis Methods**

#### **1.4.1. General Methods**

Analyses will be conducted using SAS version 9.4 or higher or R version 4.1.2 or later. Tabulations will summarize for the immunogenicity parameter over time and treatment group for data collected during the dose escalation phase, and by dose and tumor type for the expansion phase.

For categorical variables, summary tabulations of the number and percentage of patients within each category (with a category for missing data) of the parameter will be presented. For continuous variables, the number of patients, mean, median, standard deviation (SD), minimum, and maximum values will be presented. In addition, geometric mean and % CV will be presented. Summary statistics will be presented, as well as confidence intervals (CIs) on selected parameters, as described in the sections below. Tables will display dose cohorts in the column headings.

This study is primarily descriptive in nature; therefore, formal statistical hypothesis testing will be limited. Data will be presented by patient in data listings and summarized by dose cohort.

All output will be incorporated into Microsoft Word or Excel files, or Adobe Acrobat PDF files, sorted and labeled according to the International Conference on Harmonisation (ICH) recommendations, and formatted to the appropriate page size(s).

Except if noted, listings will be presented by dose cohort. Within each dose cohort, patients will be ordered by patient ID number, mutation (mKRAS / mNRAS) and within each patient, the data will be ordered by ordinal visit / week.

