## **2. STUDY ANALYSES**

### **2.1. Immunogenicity Analysis**

Cellular responses will be characterized by:

- Ex vivo Intracellular cytokine staining
- In Vitro stimulated Intracellular cytokine staining
- Ex vivo Fluorospot
- In vitro stimulated Fluorospot
- Ex vivo Dextramer
- In vitro stimulated Dextramer

Response will be determined in two ways

- Method 1 – For subjects who are negative (below the limit of quantification) at baseline and have a detectable post baseline value (above the limit of quantification) will be considered a responder. For subjects who have detectable baseline values, a two-fold increase from baseline will be considered a responder.
- Method 2 (Fluorospot only)– distribution free resampling (DFR) will be applied using the methods described by Moodie et al 2010. A minimum threshold value of 2-fold difference between control and experimental wells will be assessed.

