### **4.2. Data Listing to be Generated**

Listing 1	Ex Vivo Fluorospot
Listing 2	In Vitro stimulated Fluorospot
Listing 3	Ex Vivo Intracellular Cytokine Staining
Listing 4	In Vitro stimulated Intracellular Cytokine Staining
Listing 5	Ex Vivo Dextramer
Listing 6	In Vitro stimulated Dextramer
Listing 7	ctDNA – Signatera Assay
Listing 8	ctDNA – Sysmex Assay

*Elicio Therapeutics, Inc.*  
*Addendum: Immunogenicity and ctDNA Analysis Plan, Protocol ELI-002-001*  
*February 6, 2023, Version 1.0*

---

Table 1  
 Summary and Change from Baseline for ex Vivo Fluorospot  
 (Immunogenicity Population)

Analyte	Antigen	Visit	Value	Statistic	(N=xx)	(N=xx)	(N=xx)	Cohort 1	Cohort x	Cohort x																															
IFNg	[see programming note]		Baseline (1)	Actual	N [2]	Mean (SD)	Median	Min,Max	xx.x	--																															
											N Undetectable [3]	xx.x, xx.x x																													
													Visit x	Actual	N	Mean (SD)	Median	Min,Max	xx xx.x	(xx.xx)	xx.xx																				
																						N Undetectable [3]	xx.x, xx.x x																		
																								Fold Change from Baseline	N	Mean (SD)	Median	Min,Max													
																													Response 1 [4,5] Response	N(%)											
																															2 [4,6]	N(%)									
																																	Repeat for GrB IFNg+/GRB+								
																																	Total [7]								

Results are summarized using the mean of normalized, background subtracted replicates

[1] Baseline is based on Visit 2 result

[2] N reflects the number of patients with detectable result.

[3] Number of subjects with results below the limit of detection. [4] Denominator is number of subjects with results at visit

[5] Response is defined as having a two-fold increase from baseline.

[6] Response is based on bootstrap method described by Moodie [2010] testing for 2-fold difference from the control wells

[7] Total Analyte is the sum of IFN, GrB, and IFN/GrB results for each analyte.

Programming note: For each analyte, antigens will include G12R, G12D, G12V, G12C, G12A, G12S, G13D, total mKRAS (sum of G12R, G12D, G12V, G12C, G12A, G12S and G13D antigens), Master mix NS will not be included in table but will be in the listing.

PROGRAM NAME: XXX

DATE: HH:MM/DDMMYY

Elicio Therapeutics, Inc.  
Protocol ELI-002-001

Confidential

Page 1 of x

Table 2

Summary and Change from Baseline for In vitro stimulated (IVS) Fluorospot  
(Immunogenicity Population)

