(1) response is defined as decrease from baseline or undetectable value. (2) Duration is calculated as the date of the first response until the date where the ctDNA is detectable or greater than baseline value. (3) Doubling time is the time until the ctDNA has increase 2-fold from nadir.

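### SAP Table 8 labels relative change as fold change, so reported fold-change values come out 1 below the post/baseline ratio and a doubling prints as 1

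*SAP*

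**What the plan says.** SAP section 12.1, Table 8, under the baseline derivations, defines change from baseline as a difference and then fold change from baseline as "Post baseline value – Baseline value)/Baseline value" (the numerator is bracketed). Further down, the same table uses percent change from baseline for biomarker reduction and clearance, with -100% meaning clearance.

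Fold change is a named measure. Protocol section 6.2.3 and SAP section 9.1.3 make it one of two measures of immunogenicity, an exploratory endpoint, and protocol section 11.4 calls for it for ctDNA at each timepoint. The immunogenicity and ctDNA addendum attached to the SAP reports it in the table shells for Fluorospot and ICS, in the dextramer tables that repeat the ICS layout, in the ctDNA table, and in the listings. Neither the protocol nor the addendum gives a formula.

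The addendum's responder rule, Method 1 in section 2.1, has two parts. A subject below the limit of quantification at baseline responds if they "have a detectable post baseline value (above the limit of quantification) will be considered a responder". For the rest: "For subjects who have detectable baseline values, a two-fold increase from baseline will be considered a responder". The footnote to the addendum's Table 1 repeats this for Response 1: "Response is defined as having a two-fold increase from baseline".

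**The concern.** In ordinary usage a fold change is a ratio: 1 means no change and 2 means a doubling. The Table 8 expression is the proportional change, which SAP Table 8 elsewhere calls percent change once it is multiplied by 100. The SAP therefore has two names for one quantity and no definition of the ratio.

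Two things are at stake. The first follows from applying the SAP literally: a reader who sees a mean fold change of 1.0 will take it as no change, when it stands for a mean post/baseline ratio of 2. The second is conditional. In the addendum's Table 1 the fold-change row sits directly above Response 1. A programmer who derives Response 1 from that row with a cut-off of 2 would apply a stricter rule than the text describes.

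**Working it through.** **Inputs.** The formula is from SAP Table 8. The responder rules are from addendum section 2.1 and the Table 1 footnotes. The ctDNA rules are from addendum section 2.2 and the Listing 7 footnotes. There is no sample-size or power figure to reproduce for this point.

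**Step 1, the offset.** With baseline *b* and post-baseline value *p*, Table 8 gives (p - b)/b = p/b - 1. The offset from the ratio is exactly 1 for every subject and visit. In a summary table the mean, median, minimum and maximum all fall by 1, and the standard deviation is unchanged.

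**Step 2, numbers.** Take b = 10 for illustration; the result does not depend on this choice.

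| p | Ratio p/b | Table 8 value | Table 8 value ≥ 2 | Ratio ≥ 2 |
|---|---|---|---|---|
| 5 | 0.5 | -0.5 | no | no |
| 10 | 1.0 | 0 | no | no |
| 15 | 1.5 | 0.5 | no | no |
| 20 | 2.0 | 1.0 | no | yes |
| 25 | 2.5 | 1.5 | no | yes |
| 30 | 3.0 | 2.0 | yes | yes |
| 40 | 4.0 | 3.0 | yes | yes |

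**Step 3, the conditional effect on Method 1.** Requiring (p - b)/b ≥ 2 means p ≥ 3b. The two rules disagree only for 2b ≤ p < 3b, and only for subjects with a detectable baseline, because the others are classified by the limit-of-quantification rule. On the Table 8 scale the cut-off equivalent to a doubling is 1. If 3 to 6 subjects in a cohort have results, one reclassified subject moves that cohort's Response 1 rate by 1/6 = 17 to 1/3 = 33 percentage points.

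**Step 4, which other rules depend on the Table 8 variable.** Each was checked for its reference value.

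- Method 2 (distribution-free resampling): "A minimum threshold value of 2-fold difference between control and experimental wells will be assessed". The R call sets the threshold at log10(2), which is a ratio of 2. The addendum's printed example is for the equality version of the method. Its first row gives (23 + 22 + 24)/3 - (9 + 5 + 8 + 3 + 5 + 7)/6 = 23 - 6.1667 = 16.8333, matching the printed 16.83333. No baseline value enters.
- ctDNA doubling: section 2.2 counts weeks to the visit at which ctDNA first doubles, and the Listing 7 footnote says "Doubling time is the time until the ctDNA has increase 2-fold from nadir". With baseline 10, nadir 2 and a later value of 4, the rise from nadir is 4/2 = 2-fold, while the Table 8 value against baseline is (4 - 10)/10 = -0.6. The two are unrelated.
- The two-fold mark in Listing 7 is attached to the column for change from the previous value, not from baseline.
- ctDNA response is any fall below baseline or an undetectable result, with no fold threshold.

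Only Method 1, shown as Response 1, is measured against baseline.

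**The case against.** The strongest reply is that Table 8 may not govern the addendum. SAP section 14.0 places the ctDNA and immunogenicity analyses outside the main document, and the addendum has its own populations, baseline definitions and response rules. It points back to the protocol and SAP for background, design, sample size, dosing and sample collection, and not for derived variables. Method 1 is also stated directly in words and never cites the Table 8 variable. This stands as far as it goes: misclassification of responders is not shown. It does not remove the labelling problem. The addendum reports fold change without defining it, and Table 8 is the only definition to turn to.

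Three stronger readings are tempting, and the documents do not support them.

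- A reader might infer that every two-fold rule in the addendum is misapplied. Step 4 of the working shows that all but Method 1 use another reference or no fold threshold.
- A reader might infer that geometric means break down, since Table 8 values are zero or negative for stable or falling results and addendum section 1.4.1 says "In addition, geometric mean and % CV will be presented". That sentence covers continuous variables generally, and the table shells show no geometric mean for fold change. A cleared sample would also give a ratio of 0, so the ratio alone would not cure the problem.
- A reader might infer that the recommended Phase 2 dose is affected. The plan says only that pharmacodynamic data are considered. It does not name the Method 1 rate as an input or set a threshold for it.

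**Conclusion.** Wrong as written, and narrow. The Table 8 formula is relative change under the label of fold change. If it is followed, every fold-change-from-baseline value in the addendum's outputs is 1 lower than the post/baseline ratio. This assumes only that Table 8 is applied where the addendum is silent.

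The further effect, in which Method 1 requires a tripling and misses rises from 2-fold to under 3-fold, needs the extra assumption that Response 1 is programmed from the Table 8 variable with a cut-off of 2. The biomarker reduction and clearance endpoint is untouched, because it is defined on percent change, for which the Table 8 expression times 100 is the right quantity.

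**What to change.** In SAP Table 8, define fold change from baseline as post-baseline value divided by baseline value. Keep (post - baseline)/baseline × 100 under the name percent change, which the biomarker rows of the same table already use. In addendum section 2.1 and the Table 1 footnote, write the Method 1 rule for detectable baselines as post/baseline ≥ 2, and leave the limit-of-quantification rule as it is. A cross-reference from the addendum to Table 8 would settle which definition governs.

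The cost is a few lines of SAP wording and the matching program lines. No data collection or analysis set changes.

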### **6.2.2. Secondary Endpoint**

The secondary endpoint of Phase 1 is:

- To report the proportion of subjects with ctDNA reduction and clearance, defined as reduction or clearance in ctDNA compared to baseline, or if ctDNA was not detectable at baseline, serum tumor biomarker (such as CA19-9, CEA, and CA-125) reduction and clearance compared to baseline

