## 11. CLINICAL ACTIVITY, IMMUNE ASSESSMENTS, AND SUBJECT REPORTED OUTCOMES

Clinical activity, immune assessments, and PROs will be collected according to the Schedule of Assessments (Table 11, Table 12, Table 13, Table 14, Table 15, and Table 16).

Median RFS and 1-year RFS rate will be assessed through CT imaging with contrast as assessed by the site investigators using iRECIST criteria [Seymour et al, 2017]; subjects will be followed for OS. Unscheduled CT or MRI imaging may be performed at any time, if the investigator determines that there are clinical signs of disease progression.

In addition, biomarker response rate will be based on the percentage of subjects achieving biomarker reduction or clearance, as measured by the absence or decrease of ctDNA from baseline and the duration of ctDNA clearance and/or reduction, or if ctDNA was not detectable at baseline, serum tumor biomarker (such as carbohydrate antigen [CA]19-9, carcinoembryonic antigen [CEA], and CA-125) reduction and clearance compared to baseline will be recorded. T cell responses in PBMCs will be assessed by immune assays such as IFN $\gamma$  Fluorospot, ICS, and/or dextramers.

Immune responses will be correlated to clinical efficacy parameters.

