#### 9.1.2 Phase 1 Secondary Endpoint

- To report the proportion of subjects with ctDNA reduction and clearance, defined as reduction or clearance in ctDNA compared to baseline, or if ctDNA was not detectable at baseline, serum tumor biomarker (such as CA19-9, CEA, and CA-125) reduction and clearance compared to baseline

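### SAP Table 8 picks each subject's biomarker by its post-baseline result, against the ctDNA-first secondary endpoint; the SAP neither declares this nor says which rule gives the endpoint rate

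*SAP*

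**What the plan says.** **The endpoint.** Protocol 6.2.2 sets the aim as "To report the proportion of subjects with ctDNA reduction and clearance, defined as reduction or clearance in ctDNA compared to baseline", and SAP 9.1.2 completes the rule: "or if ctDNA was not detectable at baseline, serum tumor biomarker (such as CA19-9, CEA, and CA-125) reduction and clearance compared to baseline". The marker is therefore settled by baseline status. Protocol 11 repeats the order ("and the duration of ctDNA clearance and/or reduction, or if ctDNA was not detectable at baseline, serum tumor biomarker"), as does SAP 11.1 ("biomarker (ctDNA, or if ctDNA was not detected at baseline, serum tumor biomarker) clearance/reduction is observed").

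**The derivation.** The note that opens the biomarker block of SAP Table 8 reads: "All reporting will select the biomarker (ctDNA, CEA, or CA-19) which contains the best (i.e., largest decrease post-baseline) result per subject". If nothing fell, the smallest increase is taken. Priority for ctDNA appears only here: "If there is a tie for best response across biomarkers, select ctDNA first". Reduction is any negative percent change from baseline. Clearance is "Define as the percent change from baseline of the on-study ctDNA, or CA19-9, or CEA that achieved -100" (per cent). The chosen marker also fixes the end dates of reduction and clearance, and SAP 13.6 carries the waterfall marker over to the swimmer plots.

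**Other passages that bear on it.** Protocol 13.3.3.2 and the efficacy paragraph of the synopsis define response by ctDNA or a serum tumor biomarker, with no order. Protocol 13.3.3.2 also counts subjects without a response for any reason, including missing data, as non-responders. Protocol 13.3.3.3 treats a serum marker as cleared once it is at or below the upper limit of normal (ULN). Addendum 2.2 defines a ctDNA-only responder rate, analysed separately for the two laboratories. SAP 14 lists several changes from the protocol, but not the marker selection.

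**The concern.** A rule that looks at the outcome before choosing the measurement gives a subject two or three chances to respond. Take a subject with detectable ctDNA at baseline that only rises, and a CA19-9 that dips slightly once. Under SAP 9.1.2 that subject is a non-responder; under Table 8, a reduction responder. Both rules stand in the same SAP, and a programmer cannot follow both.

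What is at stake is the estimate of the only secondary endpoint. The SAP plans no formal testing here, so this is not a type I error problem. But SAP 13.1 says the efficacy summaries are meant to inform the design of later studies, and an upward-biased proportion would be carried into them.

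Two linked gaps sit in the same table. CA-125, which the endpoint names and the visit schedule assigns to ovarian subjects, is not among the Table 8 markers. And -100% for a serum marker requires a recorded zero, a much stricter test than the protocol's ULN.

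**Working it through.** The plan states no expected rate for this endpoint, so there is no figure to reproduce.

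**Step 1: the rules side by side.**

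| Source | Marker used | Fixed by |
|---|---|---|
| Protocol 6.2.2, Protocol 11, SAP 9.1.2, SAP 11.1 | ctDNA, else serum | baseline status |
| Protocol 13.3.3.2, synopsis | ctDNA or serum | no order given |
| SAP Table 8 | best of ctDNA, CEA, CA19-9 | post-baseline result |
| Addendum 2.2 | ctDNA only, per laboratory | no serum fallback |

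**Step 2: direction.** For a subject with detectable baseline ctDNA, ctDNA stays among the Table 8 candidates. If ctDNA fell, the best marker fell too, so no responder is lost and some may be gained. For clearance, ctDNA at -100% cannot be beaten and wins ties; a serum marker adds clearance only if a zero is recorded.

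**Step 3: draws available.** Counted from first dose (visit day minus 57), the protocol schedule gives 16 post-baseline ctDNA draws (days 21, 119, 139, 174, 202, and so on to 1070). It gives 12 serum draws (days 91, 202, 342, and so on to 1070). Baseline is Visit 3 for ctDNA and Visit 2 (day -31) for serum. Actual counts will be lower: Table 8 says "Results will not be considered if a subject has already started taking subsequent anti-cancer therapy", and SAP 14 records early termination of long-term follow-up.

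**Step 4: size under assumed behaviour**, with one serum marker independent of ctDNA. For flat markers, the chance that at least one of k later values lies below baseline is k/(k+1). With k ctDNA and m serum draws, best-of gives 1 - 1/((k+1)(m+1)). The rising-marker rows use lognormal noise with CV 30% and 400,000 simulated subjects. Where serum is flat they reduce to 1 - (1 - p)/(m+1), with p the ctDNA-only rate.

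| Assumption | Draws (ctDNA, serum) | ctDNA first | Best of two | Gain (points) |
|---|---|---|---|---|
| Both flat | 16, 12 | 16/17 = 0.941 | 1 - 1/221 = 0.995 | +5 |
| Both flat | 8, 4 | 8/9 = 0.889 | 1 - 1/45 = 0.978 | +9 |
| Both flat | 4, 1 | 4/5 = 0.800 | 1 - 1/10 = 0.900 | +10 |
| Both double every 90 days | 4, 1 | 0.35 | 0.36 | +1 |
| Both double every 180 days | 4, 1 | 0.48 | 0.55 | +7 |
| ctDNA doubles every 90 days, serum flat | 4, 1 | 0.35 | 1 - 0.65/2 = 0.675 | +32 |
| Same | 5, 2 | 0.35 | 1 - 0.65/3 = 0.78 | +43 |

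The +32 becomes +39 at CV 15% and +28 at CV 50%. Correlation between markers shrinks the gain. For a single visit where each marker has an even chance of falling, best of two gives 0.75 if the markers are independent and 0.60 at correlation 0.8, against 0.50 for ctDNA alone.

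**Step 5: denominator.** SAP 13.8.2 puts tumor biomarkers in the sample-available set. If m of N treated subjects have no usable sample, that multiplies the rate by N/(N - m) relative to counting them as non-responders. With the planned N of 18 and m assumed to be 1, 2 or 3, the factor is 1.06, 1.13 or 1.20. N may be larger, since the SAP adds Cohorts 4 and 5.

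**The case against.** The strongest reply is that the protocol does not speak with one voice. Read literally, Protocol 13.3.3.2 counts a fall in either marker. With an any-decrease threshold, that classifies the same subjects as Table 8 does, as long as the marker is ctDNA, CEA or CA19-9. This stands: the protocol wording also needs reconciling. It does not remove the conflict with Protocol 6.2.2 and SAP 9.1.2, where the endpoint is defined.

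Second, a reader might infer that Table 8 is bound to produce the secondary-endpoint rate. The documents do not show that. The only outputs the SAP text names for the selected marker are waterfall and swimmer plots, the table shells are in a separate document, and SAP 14 sends ctDNA analyses to the addendum. What can be said is that the Table 8 note covers all reporting and that nothing assigns the endpoint to another rule. Addendum 2.2 cannot supply it alone, because it has no serum fallback.

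Third, the Version 3.0 entry in the SAP revision history does mention biomarker reduction and clearance definitions. That is partial disclosure; it does not describe a departure from the protocol. A reader might also infer from its August 2024 date, in an open-label trial, that results shaped the rule. Nothing in the documents shows this.

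Fourth, it is tempting to read SAP 13.6.1 and 13.8.2 as contradicting each other on the analysis set. They do not: the full-analysis-set default yields where another section says otherwise, and 13.8.2 does. The real tension is with the missing-as-non-response rule in Protocol 13.3.3.2.

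**Conclusion.** The point holds as an undeclared conflict between two marker rules, with the endpoint rule left unstated. The direction is certain for subjects with detectable baseline ctDNA: best-of-markers keeps or raises the reduction rate. The size is not known. It runs from about +1 point to +30 or more, and the large figures need ctDNA to rise quickly while the serum marker stays flat. A reader should not take them as the expected bias.

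The figures assume independent noise and one serum marker. Table 8 ranks both CA19-9 and CEA for PDAC and CRC subjects. If both are measured, the gain could be larger, and subjects judged on serum alone could gain too. The missing CA-125 and the -100% serum criterion work the other way and may understate individual results. The any-decrease threshold is the protocol's own and is not at issue.

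This should be fixed before the final analysis. The harm is limited by the descriptive status of the endpoint, the subject listings and the separate ctDNA-only rate in the addendum.

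**What to change.** 1. For the secondary-endpoint proportion, replace the Table 8 selection note with the SAP 9.1.2 order: one marker per subject, fixed at baseline. Use ctDNA if detectable, otherwise one serum marker named before analysis, including CA-125 for ovarian subjects. The schedule maps no marker to NSCLC, cholangiocarcinoma or gallbladder cancer; there, use the serum marker that met the eligibility criterion. Reconcile the wording of Protocol 13.3.3.2 with this order.
2. Define serum clearance as a fall to at or below ULN in subjects whose baseline was above ULN. The baseline condition is needed because inclusion criterion 4b admits rising values without a ULN floor, so a marker already in the normal range could otherwise count as cleared.
3. Count treated subjects with missing post-baseline data as non-responders, on the authority of Protocol 13.3.3.2. Keep the sample-available set as supportive.
4. State that this rule gives the secondary-endpoint rate and that Addendum 2.2 is a separate ctDNA-only summary.
5. Keep best-of-markers only for the waterfall and swimmer plots, labelled exploratory and selected on outcome. List any remaining departure in SAP 14.

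The cost is SAP wording, one derivation and a clarification of Protocol 13.3.3.2; no new data are needed. The reported reduction rate may be lower, while the CA-125 and ULN changes could raise some individual results.
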